2. PROTOCOL SYNOPSIS

Name of Sponsor/Company: Braeburn Pharmaceuticals
Name of Investigational Products: CAM2038 q1w (buprenorphine FluidCrystal [®] once-weekly injection depot) CAM2038 q4w (buprenorphine FluidCrystal [®] once-monthly injection depot)
Name of Active Ingredient: Buprenorphine
Study Title: An Open-Label, Multicenter Study Assessing the Long-Term Safety of a Once-Weekly and Once-Monthly Long-Acting Subcutaneous Injection Depot of Buprenorphine (CAM2038) in Adult Outpatients with Opioid Use Disorder
Objectives: Primary Objective: To demonstrate the safety and tolerability of CAM2038 products in 12-month (48-week) buprenorphine (BPN) treatment in adult outpatients with opioid use disorder. Secondary Objectives: To evaluate efficacy of CAM2038 through several efficacy parameters, including urine toxicology, signs and symptoms of withdrawal and cravings in adult outpatients with opioid use disorder.
Methodology: This is an open-label multi-center, 12-month safety study, consistent with standard practice for long-term safety studies. This one year safety study will utilize CAM2038 q1w (once weekly) and q4w (once monthly) and will have 3 phases: Screening, Treatment, and Follow-up. Patients who are currently taking sublingual (SL) BPN (weekly or monthly prescription visits) or individuals who are actively seeking BPN treatment but who have not yet begun a treatment regimen, may be eligible for the study. Following Screening, qualified subjects meeting inclusion criteria and not meeting exclusion criteria will be initiated on either CAM2038 q1w or q4w, based on their current treatment status (qualified subjects currently on SL BPN or seeking BPN treatment). Qualified subjects will be initiated or transitioned to CAM2038 q1w or q4w as follows: 
▪ Initiation of BPN treatment – initiate with CAM2038 q1w▪ Currently receiving SL BPN treatments – transfer to corresponding CAM2038 q1w or q4w dose Subjects will be allowed to receive supplemental BPN during the study with booster SC injections of CAM2038 q1w 8 mg at the discretion of the Investigator. Dose adjustments (up or down titrations) will also be allowed at scheduled visits. The study will end when at least 100 subjects have been exposed to CAM2038 for 12 months (48 weeks). All subjects will be transitioned back to usual care and followed for an additional 4 weeks (up to Week 52). To ensure adequate enrollment and address potential inconvenience to subjects, all subjects will receive appropriate compensation for time and travel expenses related to attendance at study visits. All costs of medications and counseling will also be covered.

Name of Sponsor/Company: Braeburn Pharmaceuticals
Name of Investigational Products: CAM2038 q1w (buprenorphine FluidCrystal [®] once-weekly injection depot) CAM2038 q4w (buprenorphine FluidCrystal [®] once-monthly injection depot)
Name of Active Ingredient: Buprenorphine
Number of Subjects (Planned): The study will enroll approximately 228 subjects (new entrants to CAM2038 treatment) with estimated dropout rate of approximately 50% to ensure at least 100 subjects are exposed to CAM2038 for up to 48 weeks. The study will end after at least 100 subjects have been exposed to CAM2038 for 48 weeks.
Diagnosis and Main Criteria for Inclusion: This study will enroll adult outpatients with opioid use disorder as defined by the Diagnostic and Statistical Manual of Mental Disorders – Fifth Edition (DSM-V). Subjects must meet one of the following criteria for BPN treatment history: 
Voluntarily seeking treatment for opioid use disorder (not currently on BPN treatment for at least last 60 days but seeking BPN treatment), or;Currently on SL BPN treatment
Investigational Product, Dosage and Mode of Administration: CAM2038 q1w: buprenorphine FluidCrystal [®] subcutaneous (SC) injection depot for once weekly administration (50 mg/mL) at doses of 8, 16, 24 and 32 mg (buprenorphine base) (0.16, 0.32, 0.48 or 0.64 mL SC injection). CAM2038 q4w: buprenorphine FluidCrystal [®] SC injection depot for once monthly administration (356 mg/mL) at doses of 64, 96, 128 or 160 mg (buprenorphine base) (0.18, 0.27, 0.36 or 0.45 mL SC injection).
Reference Therapy, Dosage and Mode of Administration: This is an open-label study, no reference therapy (placebo or active comparator) will be administered.
Duration of Study: This is a 12-month (48-week) treatment study. Subject with no previous exposure to CAM2038 will receive treatment for up 48 weeks.

Name of Sponsor/Company: Braeburn Pharmaceuticals
Name of Investigational Products: CAM2038 q1w (buprenorphine FluidCrystal® once-weekly injection depot) CAM2038 q4w (buprenorphine FluidCrystal® once-monthly injection depot)
Name of Active Ingredient: Buprenorphine
Criteria for Evaluation: Safety Endpoints: 
▪ Adverse events (AEs) and serious adverse events (SAEs)▪ Clinical laboratory tests▪ Electrocardiogram (ECG)▪ Vital signs▪ Physical and injection site examinations▪ Concomitant medications Efficacy Measures: 
▪ Urine toxicology results for illicit opioids▪ Self-reported illicit opioid use▪ Retention (%) in treatment▪ Work Productivity and Activity Impairment Questionnaire-General Health (WPAI-GH)▪ EQ-5D-5L Health Questionnaire▪ Patient Satisfaction Scale▪ Measures of opioid withdrawal:
○ Clinical Opiate Withdrawal Scale (COWS)○ Subjective Opiate Withdrawal Scale (SOWS)▪ Measures of opioid craving:
○ Desire to Use visual analogue scale (VAS)○ Need to Use VAS▪ Urine toxicology results for other drugs of abuse
Statistical Methods (Data Analysis): 
Two safety populations will be considered: the Full Exposure Safety population and the Overall Safety Population. The Full Exposure Safety Population will include all subjects who have been exposed to CAM2038 for 48 weeks. The Overall Safety Population will include all subjects who received at least one CAM2038 treatment. Exposure and safety summaries will be presented for both populations.
 
Adverse events will be coded by primary system organ class (SOC) and preferred term according to the Medical Dictionary for Regulatory Activities (MedDRA), and summarized by number and percent of subjects in each primary SOC and preferred term. Summaries of these AE subsets will be presented for relationship to study drug, intensity, seriousness, AEs or SAEs leading to discontinuation and AEs occurring in 5% or greater of any treatment group (by preferred term). Frequencies for deaths and

Name of Sponsor/Company: Braeburn Pharmaceuticals
Name of Investigational Products: CAM2038 q1w (buprenorphine FluidCrystal® once-weekly injection depot) CAM2038 q4w (buprenorphine FluidCrystal® once-monthly injection depot)
Name of Active Ingredient: Buprenorphine
hospitalizations will also be summarized. Data for clinical laboratory tests, ECG, vital signs, and physical and injection site examinations will be summarized using standard descriptive and change from baseline statistics. Shift tables and tabular summaries of abnormalities will be provided, where appropriate. Medications will be coded using the World Health Organization Drug dictionary and summarized using descriptive statistics. By-subject listings will be provided for all safety data. Exploratory efficacy measures will be summarized by visit using standardized descriptive statistics and listed by subject.

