9.3.4. Quality of Life Questionnaires and Patient Satisfaction Scale

Two quality of life questionnaires will be provided to subjects for completion:

- Work Productivity and Activity Impairment Questionnaire-General Health (WPAI-GH) (Reilly Associates).
- EQ-5D-5L Health Questionnaire (EuroQOL Group Association).

These are to be completed on a monthly basis, approximately every four weeks at the subjects scheduled visit.

A patient satisfaction scale will be provided to subjects for completion at month 6 and month 12 (EOT).

Copies of the WPAI-GH, EQ-5D-5L and patient satisfaction scale is provided in the Study MOP.

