10.0 EFFICACY ANALYSES

10.1.1 EFFICACY VARIABLES

This is a long-term safety study and efficacy evaluation is not the primary objective of the study. All efficacy variables will be summarized using the efficacy population. The efficacy variables will include the following:

- Urine toxicology results for illicit opioids
- Self-reported illicit opioid use
- Retention (%) in treatment (identical to exposure)
- Retention (%) in study
- Measures of opioid withdrawal:
 - Clinical Opiate Withdrawal Scale (COWS)
 - Subjective Opiate Withdrawal Scale (SOWS)

- Measures of opioid craving:
 - Desire to Use Visual Analogue Scale (VAS)
 - Need to Use VAS
- Urine toxicology results for other drugs of abuse
- Work Productivity and Activity Impairment Questionnaire General Health (WPAI-GH)
- EQ-5D-5L Health Questionnaire
- Patient Satisfaction Scale

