10.1.6 MEASURES OF OPIOID WITHDRAWAL

Measures of withdrawal include COWS and SOWS. The COWS is comprised of 11 items, each with a score of 0 through 4 or 5. Higher scores are associated with greater withdrawal symptoms. The items are meant to be objective measures of a patient's withdrawal symptoms (e.g., resting pulse rate). The SOWS is comprised of 16 items each with a score of 0 through 4. Higher scores are associated with greater withdrawal symptoms. The items are statements that are evaluated by the patient and are therefore subjective (e.g., I feel anxious, 0 = not at all, 1 = a little, 2 = moderately, 3 = quite a bit, 4 = extremely).

If there are ≥ 3 (i.e., $\geq 20\%$) missing items in the COWS scale at a given visit or ≥ 4 (i.e., $>20\%$) missing items in the SOWS scale at a given visit, the COWS/SOWS score for that visit will be missing. If there are 1 or 2 missing items for the COWS assessment then the total of the non-missing items will be calculated and the product of the calculated total and $11/(11 - \# \text{ missing})$ will be used for the COWS score

for that visit. If 3 or fewer items are missing for the SOWS score then the total of the non-missing items will be calculated and the product of the calculated total and $16/(16 - \# \text{ missing})$ will be used for the SOWS score.

COWS and SOWS data will be presented by visit. Data will also be presented as change from baseline by subtracting the baseline values from the post-baseline values. Negative changes are thus indicative of improvement.

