10.1.9 WORK PRODUCTIVITY AND ACTIVITY IMPAIRMENT QUESTIONNAIRE GENERAL HEALTH (WPAI-GH)

Data for WPAI-GH will be presented by item over time.

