10.1.10 EQ-5D-5L HEALTH QUESTIONNAIRE

Data for EQ-5D-5L will be presented over time.

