| TABLE 14.2.2.3 | Summary of Mean Percentage of Urine Toxicology Results for Illicit Opioids Use Supported by Self-Reported Illicit Opioid Use by Treatment Status at Baseline (New to Treatment [Yes/No]) |
| TABLE 14.2.2.4 | Summary of Mean Percentage of Urine Toxicology Results for Illicit Opioid Use Without Self-Reported Illicit Opioid Use by Treatment Status at Baseline (New to Treatment [Yes/No]) (Efficacy Population) |
| TABLE 14.2.3.1 | Summary of Self-Reported Illicit Opioid Use over Time (Efficacy Population) |
| TABLE 14.2.3.2 | Summary of Mean Percentage of Self-Reported Illicit Opioid Use (Efficacy Population) |
| TABLE 14.2.4.1 | Summary of Retention (%) in Treatment over Time (Efficacy Population) |
| TABLE 14.2.4.2 | Time to End of Retention in Treatment (Efficacy Population) |
| TABLE 14.2.5.1 | Summary of Retention (%) in Study over Time (Efficacy Population) |
| TABLE 14.2.5.2 | Time to End of Retention in Study (Efficacy Population) |
| TABLE 14.2.4.3 | Summary of Retention (%) in Treatment over Time by Treatment Status at Baseline (New to Treatment [Yes/No]) (Efficacy Population) |
| TABLE 14.2.4.4 | Time to End of Retention in Treatment by Treatment Status at Baseline (New to Treatment [Yes/No]) (Efficacy Population) |
| TABLE 14.2.6 | Summary of Clinical Opiate Withdrawal Scale (COWS) over Time (Efficacy Population) |
| TABLE 14.2.7 | Summary of Subjective Opiate Withdrawal Scale (SOWS) over Time (Efficacy Population) |
| TABLE 14.2.8 | Summary of Desire to Use VAS over Time (Efficacy Population) |
| TABLE 14.2.9 | Summary of Need to Use VAS over Time (Efficacy Population) |
| TABLE 14.2.10.1 | Summary of Urine Toxicology Results for Other Drugs of Abuse over Time (Efficacy Population) |
| TABLE 14.2.10.2 | Summary of Mean Percentage of Urine Toxicology Results for Other Drugs of Abuse (Efficacy Population) |
| TABLE 14.2.11 | Summary of Work Productivity and Activity Impairment Questionnaire General Health (WPAI-GH) by Item over Time (Efficacy Population) |
| TABLE 14.2.12 | Summary of EQ-5D-5L Health Questionnaire Data over Time (Efficacy Population) |
| TABLE 14.2.13 | Summary of Patient Satisfaction Scale Scores by Item over Time (Efficacy Population) |
| TABLE 14.3.1.1 | Summary of CAM2038 Exposure over Time (Overall Safety Population) |
| TABLE 14.3.1.2 | Summary of CAM2038 Exposure over Time (Full Exposure Safety Population) |

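### WPAI-GH and EQ-5D-5L are planned only as values over time, without the change from baseline given to COWS, SOWS and both VAS, so a changing patient mix can pass for patient change

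*Protocol*

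**What the plan says.** **Protocol.** The synopsis and Section 11.3.2 carry the same sentence for all exploratory efficacy measures: "Exploratory efficacy measures will be summarized by visit using standardized descriptive statistics and listed by subject". It applies to COWS, SOWS and the VAS as much as to the questionnaires, and Section 11.1 leaves the detail to the SAP.

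**SAP, withdrawal and craving.** Section 10.1.6 plans COWS and SOWS by visit and adds: "Data will also be presented as change from baseline by subtracting the baseline values from the post-baseline values". Section 10.1.7 does the same for the Desire to Use and Need to Use VAS.

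**SAP, questionnaires.** The whole of Section 10.1.9 is: "Data for WPAI-GH will be presented by item over time". The whole of Section 10.1.10 is: "Data for EQ-5D-5L will be presented over time". In Appendix A, Table 14.2.12 is titled "Summary of EQ-5D-5L Health Questionnaire Data over Time (Efficacy Population", and the title of Table 14.2.11 ends "WPAI-GH) by Item over Time (Efficacy Population".

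**Data collected.** Protocol Table 3 schedules both questionnaires at Screening, Day 1, monthly and end of treatment. Protocol 9.3.4 confirms the interval: "These are to be completed on a monthly basis, approximately every four weeks at the subjects scheduled visit".

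**Patients summarised.** SAP 10.1.1: "All efficacy variables will be summarized using the efficacy population". Under SAP 5.3 that means at least one dose and some post-baseline efficacy measurement. SAP 7.0 expects about 228 enrolled and 50% dropout.

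**The concern.** A table of by-visit means invites the reader to compare the last row with the first. With about half of the patients gone by then, the two rows are averages over different people. If those who stay had better (or worse) scores at the start than those who leave, the mean drifts with no change in anyone, and nothing in the planned tables separates that drift from a real gain or loss.

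A baseline gap is plausible here. The study enrols both patients already on sublingual buprenorphine and patients newly seeking treatment. The SAP lists retention and urine results by that status, but not these two questionnaires.

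What is at stake is how two exploratory patient-reported measures will be read. No hypothesis, sample size or decision rule rests on them.

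**Working it through.** **1. Is change from baseline supplied elsewhere?** SAP 6.0 (general conventions) lists descriptive statistics and does not mention change. SAP 6.1 defines baseline but does not say which measures get a change analysis. The table titles do not settle it, because the COWS, SOWS and VAS tables are also titled as over-time summaries. The deciding text is therefore 10.1.9 and 10.1.10 set beside 10.1.6 and 10.1.7, and there the contrast is clear. No completer or fixed-cohort summary of the two questionnaires is planned.

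**2. The plan's enrolment figure, used only to size the change in mix.**
- 100 / (1 - 0.5) = 200, so the stated 228 is not reproduced from 100 and 50%.
- 228 x 0.5 = 114 remaining. Exactly 100 remaining would mean dropout of 1 - 100/228 = 56.1%.
- The figure errs on the larger side and is not contested here.

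**3. Shift in the by-visit mean when no patient changes.** Let d be the dropout share, S and L the baseline means of stayers and leavers, and D = S - L.
- Mean of all at baseline = (1 - d)S + dL.
- Mean of stayers at the late visit = S.
- Apparent change = S - [(1 - d)S + dL] = d x D.
- Paired change in the stayers = 0.

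| D (assumed, in SD) | d = 50% | d = 56.1% |
|---|---|---|
| 0.1 | 0.05 | 0.06 |
| 0.2 | 0.10 | 0.11 |
| 0.3 | 0.15 | 0.17 |
| 0.5 | 0.25 | 0.28 |
| 0.8 | 0.40 | 0.45 |

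**4. Simulation check (228 patients, 4,000 replicates).**
- Dropout depends on the baseline score (logistic slope 0.5 per SD, about 50% leaving), with no true mean change: by-visit shift 0.24 SD, paired change 0.00. By the formula in step 3 this corresponds to D of about 0.24 / 0.5 = 0.48 SD.
- Dropout depends on the patient's own change (change SD 0.5, true mean zero): by-visit shift 0.12 SD, paired change 0.12 SD. Pairing gives no protection in this case.

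**5. Precision.** Stayers appear in both rows, so the rows are correlated. Take 228 patients at baseline and 114 late, within-patient correlation r, and dropout unrelated to score. In SD² units:
- By-visit difference: 1/114 + 1/228 - 2r/228 = (3 - 2r)/228.
- Paired change: 2(1 - r)/114 = (4 - 4r)/228.

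| r (assumed) | By-visit SE (SD) | Paired SE (SD) |
|---|---|---|
| 0.3 | 0.103 | 0.111 |
| 0.5 | 0.094 | 0.094 |
| 0.7 | 0.084 | 0.073 |

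Neither summary is more precise throughout. For scale, shifts of 0.10 and 0.25 SD are 1.1 and 2.7 times an SE of 0.094 SD.

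**The case against.** The case for leaving the plan alone has several parts.

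- **The measures are marginal.** Protocol 9.5 calls the efficacy endpoints exploratory, and the secondary objective names urine toxicology, withdrawal and cravings, not quality of life or work productivity. This stands and keeps the point minor. COWS, SOWS and the VAS are equally exploratory, however, and do get change from baseline.
- **The information is not lost.** Listings 16.2.6.6 and 16.2.6.7 show both questionnaires by patient, and SAP 6.0 reports n, so attrition will be visible. A reader might infer that the study cannot separate patient change from patient mix. The documents do not support that: the limit lies in the planned tables, not in the data. Table 14.1.3.2 gives baseline characteristics of the fully exposed patients, but those listed in SAP 8.2 do not include these questionnaires.
- **The gap D has no source.** Neither its size nor its sign is known. Patients with no post-baseline efficacy data are outside the efficacy population, so the dropout share that applies may be somewhat below 50%. Both points stand; the shift is an illustration.
- **Paired change is no cure for dropout.** This also stands, as the second simulation shows.

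Two further inferences are tempting and unsupported. One is that the by-visit comparison is less precise than the paired one; step 5 shows equal standard errors at r = 0.5 and either order elsewhere. The other is that the protocol sentence itself treats the questionnaires differently; it covers all exploratory measures alike, and the difference arises only in the SAP.

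**Conclusion.** The point holds as a minor inconsistency in the SAP with a practical consequence. Sections 10.1.9 and 10.1.10 omit the change from baseline that 10.1.6 and 10.1.7 specify, although the baseline is collected. At the plan's 50% dropout, about half of any baseline gap between stayers and leavers will appear as change in the by-visit mean. The range of 0.10 to 0.25 SD rests wholly on the assumed D of 0.2 to 0.5 SD. Observed-case paired change removes that component and no other: bias from dropout related to a patient's own course remains.

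**What to change.** In SAP 10.1.9 and 10.1.10 and Tables 14.2.11 and 14.2.12:

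- For numeric items and scores, add within-patient change from baseline at each monthly visit and at end of treatment, with n, a 95% CI and the baseline mean of the same patients.
- For categorical EQ-5D-5L responses, add the percentage improved, unchanged or worse than baseline.
- First settle SAP 6.1, which gives both the last value before first dose and the average of several baseline values. Both questionnaires are scheduled at Screening and Day 1, so the two rules can differ. Use whichever 6.1 then states, rather than assuming Day 1; Table 3 does not say that the Day 1 questionnaire comes before the injection.
- State beside the tables that paired change in observed cases removes baseline-level differences between stayers and leavers, but not dropout linked to a patient's own course.

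If the over-time wording was already meant to include change, one sentence in each section is enough. The cost is SAP wording and a few added table columns; no new data are needed.

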4. LIST OF ABBREVIATIONS AND DEFINITION OF TERMS

AE	Adverse event
AIDS	Acquired Immune Deficiency Syndrome
ALT	Alanine aminotransferase
AST	Aspartate aminotransferase
BPN	Buprenorphine
BPX	Buprenorphine/naloxone
CFR	Code of Federal Regulations
C _{max}	Maximum plasma concentration
C _{min}	Minimum plasma concentration
CNS	Central nervous system
COWS	Clinical Opioid Withdrawal Scale
CRF	Case Report Form (may include electronic data capture systems or paper forms)
CS	Clinically significant
CSA	Clinical Study Agreement
C-SSRS	Columbia-Suicide Severity Rating Scale
C _{trough}	Concentration levels prior to next injection
DSM-V	Diagnostic and Statistical Manual of Mental Disorders – Fifth Edition
ECG	Electrocardiogram
EDC	Electronic data capture
FC	FluidCrystal [®]
FDA	Food and Drug Administration
GCP	Good Clinical Practice
ICF	Informed consent form
ICH	International Conference on Harmonisation
IEC	Institutional Ethics Committee
INR	International normalized ratio
IRB	Institutional Review Board
IV	Intravenous
MedDRA	Medical Dictionary of Regulatory Activities
MOP	Manual of Procedures
NCS	Not clinically significant
PAC-SYM	Patient Assessment of Constipation Symptoms
PT	Prothrombin time
RBC	Red blood cell

SAE	Serious adverse event
SC	Subcutaneous
SL	Sublingual
SOC	System Organ Class
SOWS	Subjective Opioid Withdrawal Scale
SUSAR	Suspected Unexpected Serious Adverse Reaction
US	United States

5. INTRODUCTION

5.1. Background

Buprenorphine (BPN) is an opioid with mixed agonist-antagonist properties, and together with appropriate counseling and psychotherapy, has been shown to be effective in the treatment of opioid dependence. Treatment with BPN has been demonstrated to significantly reduce opioid-positive urines, i.e., to reduce illicit drug use, and increase retention of patients in outpatient treatment programs (Johnson et al, 1992; Strain et al, 1994; Schottenfeld et al, 1997; Ling et al, 1998).

CAM2038 (buprenorphine FluidCrystal[®] [FC] subcutaneous [SC] injection depot) once weekly (hereafter referred to as CAM2038 q1w) and once monthly (q4w) (hereafter referred to as CAM2038 q4w) are ready-to-use, extended release BPN products developed for opioid dependence treatment with a target of once weekly or once monthly SC dosing posology, respectively.

CAM2038 q1w and q4w were developed using the proprietary lipid-based and ambient responsive FC Injection depot technology. The principle behind the FC Injection depot is a liquid-to-gel phase transition, occurring immediately as the lipid based FC system is exposed to in vivo conditions of SC tissue. The phase transition proceeds from the outside towards the center of the injected FC by absorption of minute quantities of water. Thus, injection of CAM2038 q1w and q4w into SC tissue results in an immediate and spontaneous formation of controlled BPN release matrix providing long-acting release in vivo with a minimum initial burst release. The dual nature of the FC system, i.e., a true liquid drug product in vitro before injection and stable gel in vivo after injection, enables a ready-to-use drug product in a prefilled syringe. CAM2038 q1w and q4w are designed for convenient and safe SC injection using a prefilled syringe (from 0.15 to 0.6 mL volume depending on dose and product) including a needle safety device and with no need for mixing or temperature adjustment prior to administration. In addition, the injection volumes for CAM2038 q1w and q4w are relatively low and can be administered using a fine gauge needle (23 G). Overall, these ready-to-use, long-acting CAM2038 depots have been designed with a focus of enabling easy administration, dosing flexibility, and importantly, minimizing risks of misuse, diversion and poor patient compliance.

